8.13 Treatment presentation for tables and figures

Treatment label	Explanation	Analysis purpose
First randomised / actual treatment (Day 1)		Disposition, Demographics, Safety, Exposure
Total Dapagliflozin	All subjects 1 st randomised to / actual treatment to dapagliflozin 5mg	
Total Saxagliptin	All subjects 1 st randomised to / actual treatment saxagliptin 2.5mg	
Placebo	All subjects 1 st randomised to / actual treatment placebo	
Treatment regimen		By regimen outputs: Disposition, Efficacy
Dapagliflozin 5mg/10mg	Low/high dose regimen dapagliflozin	
Dapagliflozin 5mg	Low dose regimen dapagliflozin	
Saxagliptin 2.5mg/5mg	Low/high dose regimen saxagliptin	
Saxagliptin 2.5mg	Low dose regimen saxagliptin	
Placebo	All subjects 1 st randomised to placebo	
Second randomisation (Week 14)		Up-titration subjects analysis set outputs: Disposition, Demographics, Efficacy
Dapagliflozin 5mg	All subjects randomised at Week 14 to remain on dapagliflozin 5mg	
Dapagliflozin 10mg	All subjects randomised at Week 14 to up-titrate to dapagliflozin 10mg	
Saxagliptin 2.5mg	All subjects randomised at Week 14 to remain on saxagliptin 2.5mg	
Saxagliptin 5mg	All subjects randomised at Week 14 to up-titrate to saxagliptin 5mg	
Third randomisation (Week 32 or 40)		Randomised withdrawal subjects analysis set outputs: Disposition, Demographics, Efficacy, Safety

Treatment label	Explanation	Analysis purpose
Dapagliflozin 10mg monotherapy	All subjects randomised at Week 32/40 to withdraw background metformin and either up-titrate to dapagliflozin 10mg (if previously randomised to dapagliflozin 5mg) or to stay on dapagliflozin 10mg (if previously up-titration randomised to high-dose) or switch from placebo to dapagliflozin 10mg	
Dapagliflozin 5mg or 10mg + Metformin	All 1 st randomisation dapagliflozin subjects randomised at Week 32/40 to remain on background metformin	
Saxagliptin 5mg monotherapy	All subjects randomised at Week 32/40 to withdraw background metformin and either up-titrate to saxagliptin 5mg (if previously randomised to saxagliptin 2.5mg) or to stay on saxagliptin 5mg (if previously up-titration randomised to high-dose) or switch from placebo to saxagliptin 5mg	
Saxagliptin 2.5mg or 5mg + Metformin	All 1 st randomisation saxagliptin subjects randomised at Week 32/40 to remain on background metformin	
Placebo + Metformin	All 1 st randomisation placebo subjects randomised at Week 32/40 to remain on background metformin	
Last randomised/actual treatment		Disposition, Demographics, Safety
Dapagliflozin 10mg monotherapy	All subjects whose last randomised/actual treatment was dapagliflozin and the	

Treatment label	Explanation	Analysis purpose
	subject was randomised to withdraw background metformin	
Dapagliflozin 5mg or 10mg	All subjects whose last randomised/actual treatment was dapagliflozin and the subject remained on background metformin (if eligible for third randomisation)	
Saxagliptin 5mg monotherapy	All subjects whose last randomised/actual treatment was saxagliptin and the subject was randomised to withdraw background metformin	
Saxagliptin 2.5mg or 5mg	All subjects whose last randomised/actual treatment was saxagliptin and the subject remained on background metformin (if eligible for third randomisation)	
Placebo	All subjects whose last randomised/actual treatment was placebo and the subject remained on background metformin (if eligible for third randomisation)	
Dose at onset / actual dose and treatment taken		Dose at onset outputs: Safety (exposure, AEs, labs)
Dapagliflozin 5mg	All subjects on dapagliflozin 5mg per treatment assignments in Section 4.1.6	
Dapagliflozin 10mg	All subjects on dapagliflozin 10mg per treatment assignments in Section 4.1.6	
Total Dapagliflozin	All subjects who took Dapagliflozin based on all three randomisations	
Saxagliptin 2.5mg	All subjects on saxagliptin 2.5mg per treatment assignments in Section 4.1.6	

Treatment label	Explanation	Analysis purpose
Saxagliptin 5mg	All subjects on saxagliptin 5mg per treatment assignments in Section 4.1.6	
Total Saxagliptin	All subjects who took Saxagliptin based on all three randomisations	
Placebo	All subjects on placebo per treatment assignments in Section 4.1.6	
Highest dose taken in ST period		PK outputs
Dapagliflozin 5mg	All subjects whose highest actual dose in the ST period was dapagliflozin 5mg	
Dapagliflozin 10mg	All subjects whose highest actual dose in the ST period was dapagliflozin 10mg	
Saxagliptin 2.5mg	All subjects whose highest actual dose in the ST period was saxagliptin 2.5mg	
Saxagliptin 5mg	All subjects whose highest actual dose in the ST period was saxagliptin 5mg	

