8.4.3 Safety Analyses

The assessment of safety will be based on the analyses of AEs, vital signs, physical examinations, ECGs, hypoglycemia events, DKA events, safety laboratory evaluations, and measures of growth and maturity.

Dapagliflozin and saxagliptin will be summarized separately. Both low-dose and high-dose saxagliptin and dapagliflozin groups, respectively, will be combined for saxagliptin and dapagliflozin to provide the safety summary for overall saxagliptin and overall dapagliflozin compared to placebo. A common placebo group will be included in each summary.

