1.2 Study design

The proposed study is a 26-week Phase 3b, multicentre, randomised, placebo-controlled, double-blind, parallel-group study with a 26-week safety extension period to evaluate the safety and efficacy of dapagliflozin (5 mg and 10 mg), and, separately, saxagliptin (2.5 mg and 5 mg) in paediatric subjects with T2DM, and an additional post-study visit at Week 104 for assessment of measures of growth and maturity.

This study will consist of 4 study periods:

- (i) **Screening period.** This period starts with enrolment and ends at the start of the lead-in period.
- (ii) **Lead-in period.** During this 2-week period, subjects will be instructed on a diet and exercise program (in accordance with the American Diabetes Association [ADA] or similar local guidelines) to be followed for the study duration. Subjects will maintain their baseline types and/or doses of antidiabetic therapy throughout the study. No placebo or study medication will be provided during the lead-in period.
- (iii) **26-week double-blind short-term (ST) treatment period.** On the Day 1 visit, subjects who meet all protocol-specific enrolment and randomisation criteria will be randomised.
- (iv) **26-week double-blind long-term (LT) treatment period.** After completing the ST treatment period, all subjects will enter the 26-week LT treatment period.

The 52-week treatment period will be referenced as the ST+LT treatment period.

The **Randomised withdrawal period** is defined, for those subjects eligible for the 3rd randomisation, as the time from 3rd randomisation (Week 32 or Week 40) until end of LT period (Week 52).

Subjects who discontinue IP treatment before the end of the study treatment period will enter a non-treatment, follow-up phase in which subjects will follow their visit schedules with modified assessments until study completion.

In addition, there will be 2 post-study visits:

- (i) **Week 56** (phone visit), to assess AEs and serious adverse events (SAEs).
- (ii) **Week 104** (office visit), to assess measures of growth and maturity, height, weight, AEs and SAEs.

Approximately 243 paediatric subjects aged 10 to below 18 years of age will be randomised in a 1:1:1 ratio to receive dapagliflozin 5 mg, saxagliptin 2.5 mg, or placebo. Approximately 81 subjects will be randomised to each treatment arm.

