2.2.3 Up-titration Randomised Subjects Data Set

The Up-titration Randomised Subjects Data Set will consist of the subset of randomised subjects who are Up-titration Randomised because their HbA1c is greater than or equal to 7% at Week 12 (regardless of rescue medication initiation). This data set will be used for efficacy analysis comparing low-dose and high-dose treatment regimens in subjects who do not achieve glycaemic control (HbA1c < 7%) at Week 12. In analyses of the Up-titration Randomised Subjects Data Set, subjects will be presented in the treatment group to which they were randomised at the second randomisation.

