$$\text{Incidence rate} = 100 * \frac{n \text{ subjects with } \geq 1 \text{ event of interest}}{\text{sum}[\min(\text{exposure time}, \text{time to event})]}$$

The sum of min(exposure time, time to event) will be computed by summing up the minimum of exposure time or time to event per subject across all subjects for each treatment and dose as treated (defined in Section 2.1).

For analyses using first treatment as treated (total dapagliflozin, total saxagliptin, placebo), exposure time and time to event are defined as:

Exposure time (years) per subject is computed as (last date of exposure for that subject - date of first dose in the study + 1)/365.25. Time to event (years) for subjects having the event is computed as (date of onset of event – date of first dose in the study +1)/365.25.

For analyses using dose at onset of AE to account for the change in treatment and dose at the 2nd and 3rd randomisations, exposure time and time to event are defined as:

Exposure time (years) per subject for each treatment and dose as treated is computed as (last date of exposure to treatment and dose for that subject - date of first exposure to treatment and dose + 1)/365.25. Time to event (years) for subjects having the event whilst on the current treatment and dose is computed as (date of onset of event – date of first exposure to treatment and dose +1)/365.25.

For incidence rate analyses for events prior to rescue, if no event occurred prior to rescue medication initiation then the date of rescue medication initiation is used instead of last date of exposure.

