4.1.7 Data summaries and listings

Dapagliflozin and saxagliptin will be summarised separately. For demographics and efficacy analyses, analyses will be presented by treatment regimen (low-dose, low-dose/high-dose). In addition, for demographics, and (where specified) efficacy analyses, analyses will also be provided for overall drug (combining all doses of each drug). For safety analyses, analyses will be presented by overall drug. The common placebo group will be included in each summary.

Demographics and efficacy analyses will be based on the Randomised Subjects Data Set and the randomised treatment assignment. Selected demographics and efficacy summaries and analyses will also be provided for the Up-titration Randomised and Randomised Withdrawal Subjects Data Sets. In addition to the analyses based on the Randomised Subjects Data Set, a sensitivity analysis of the primary efficacy endpoint will be performed using the Evaluable Subjects Data Set if greater than 10% of subjects of any treatment or placebo have RPDs. Safety analyses will be based on the Treated Subjects Data Set and the actual treatment assignment.

In addition, within the analyses of dapagliflozin and saxagliptin separately, the overall (combined low-dose and high-dose) efficacy and safety analyses will be repeated for the subgroup of subjects on a stable baseline dose of metformin IR or XR (with or without insulin). For these analyses, the dapagliflozin or saxagliptin treatment groups will be combined and compared to the (common) placebo group.

Data summaries and specific analyses by study period will be restricted to the cut-off dates defined in Table 8. Comparisons are based on onset dates for events and the date of assessment for other parameters (laboratory tests, vital signs etc.). The ST and ST+LT periods start from Baseline (day of first dose in the ST period) and the Randomised Withdrawal period starts from Randomised Withdrawal Baseline (day of first dose in the Randomised Withdrawal period).

The time is included in the comparisons only if both dates being compared have the time provided.

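### The only safety tables that separate low from high dose do not compare randomised groups, and the Week 14 dose randomisation has no safety output

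*SAP*

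**What the plan says.** SAP 1.2 describes the study as one "to evaluate the safety and efficacy of dapagliflozin (5 mg and 10 mg), and, separately, saxagliptin (2.5 mg and 5 mg" each). Protocol 8.4.3 then pools doses for safety: "Both low-dose and high-dose saxagliptin and dapagliflozin groups, respectively, will be combined". SAP 4.1.7 follows: "For safety analyses, analyses will be presented by overall drug".

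SAP 8.13 lists the outputs each treatment grouping feeds:

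- Second randomisation at Week 14 (5 v 10 mg, 2.5 v 5 mg): "Up-titration subjects analysis set outputs: Disposition, Demographics, Efficacy".
- Regimen (low; low/high): "By regimen outputs: Disposition, Efficacy".
- Dose actually being taken: "Dose at onset outputs: Safety (exposure, AEs, labs").

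SAP 2.2.3 gives the purpose of the re-randomised set: "This data set will be used for efficacy analysis comparing low-dose and high-dose treatment regimens in subjects who do not achieve glycaemic control". Table 24 (SAP 8.15) has no safety row for that set or for dose assigned at Week 14.

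The dose-at-onset rates are defined in SAP 3.4.1: "For analyses using dose at onset of AE to account for the change in treatment and dose at the 2nd and 3rd randomisations", the exposure clock restarts with each dose. SAP 4.7.1.1, 4.7.1.3 and 4.7.3.4 apply this to AEs, SAEs and marked laboratory abnormalities over the combined short- and long-term period.

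**The concern.** A reader who wants to know whether 10 mg is tolerated as well as 5 mg (or saxagliptin 5 mg as well as 2.5 mg) will go to the one set of tables with a column for each dose. Those columns are not randomised groups. Nobody takes the high dose before Week 14, so the low-dose column alone carries the weeks after drug start and study entry. From Week 14 to Week 32 the high dose is taken only by children whose Week 12 HbA1c was 7% or more. From Week 32 or 40 the high-dose column also gains low-dose children who withdraw metformin and placebo children who switch to active drug, both selected on HbA1c below 7.5%.

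A difference between the columns could therefore reflect time on study, glycaemic status or loss of background metformin rather than dose. Dividing by exposure corrects for how long each dose was taken, not for when or by whom. Meanwhile the trial randomises low against high dose 1:1 within each drug, and no safety output uses it.

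**Working it through.** **1. Which safety outputs separate the doses (SAP 8.13, 4.7, Table 24)**

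| Grouping | Safety output? | Low v high dose? |
|---|---|---|
| First randomisation | Yes | No, doses pooled |
| Regimen | No | - |
| Second randomisation | No | - |
| Third randomisation | Yes | No: high-dose monotherapy v mixed dose plus metformin, or v placebo plus metformin |
| Last treatment | Yes | No, mixed-dose groups |
| Dose at onset | Yes (exposure, AEs, labs) | Yes, but not as randomised |

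**2. What the dose-at-onset columns contain**

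The plan gives no figure for this comparison. The one design number needed is 81 per arm (SAP 1.2). It agrees with the plan's own power statement: a difference of 0.75, SD 1.7 and two-sided 0.05 give 80.2%.

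Assumptions: a proportion q of 50% to 70% are Week 12 non-responders (the current documents give no rate), 52 weeks, no dropout, third randomisation ignored. Per drug:

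- Low-dose time in Weeks 0-14: 81 x 14 = 1134 person-weeks.
- Low-dose time after Week 14: 81 x (1 - q/2) x 38 = 2308.5 (q = 50%) or 2000.7 (q = 70%).
- Share of low-dose time in Weeks 0-14: 1134/3442.5 = 33%, or 1134/3134.7 = 36%.
- High-dose time: 81 x q/2 x 38 = 769.5 or 1077.3 person-weeks, none of it before Week 14.
- Responders' share of low-dose time after Week 14: (1 - q)/(1 - q/2) = 67% or 46%. Their share of high-dose time is nil under these assumptions.

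**3. Size of the distortion with no true dose effect**

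The SAP 3.4.1 rate is children with at least one event divided by the sum of the smaller of exposure and time to event. Let h be the later first-event rate per year, f times h the rate in Weeks 0-14, a = 14/52 and b = 38/52. Put S = exp(-f h a), E = 1 - S and L = (1 - q/2) S (1 - exp(-h b)). Then:

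- low-dose rate = h (E + L)/(E/f + L)
- high-dose rate = h
- high/low ratio = (E/f + L)/(E + L)

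Example with h = 1, f = 2, q = 0.5: E = 0.4164 and L = 0.2269, so the ratio is (0.2082 + 0.2269)/0.6433 = 0.68.

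| Early/later rate, f | 100 per 100 patient-years, q = 50% / 70% | 10 per 100 patient-years, q = 50% / 70% |
|---|---|---|
| 1.5 | 0.81 / 0.80 | 0.85 / 0.84 |
| 2 | 0.68 / 0.66 | 0.74 / 0.73 |
| 3 | 0.49 / 0.48 | 0.59 / 0.57 |

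The higher base rate suits a summary such as any AE. The lower one is closer to SAEs or single preferred terms.

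**4. What the third randomisation adds**

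Take q = 65%, with 30-50% of each arm on metformin only and 20-60% of those qualifying at Week 32 (all assumptions). With N eligible children per arm, extra high-dose time is (N/2 x 0.675 + N/3) x 20 person-weeks.

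- Low end: N = 81 x 0.3 x 0.2 = 4.86, giving 65 person-weeks. 65/(65 + 1000) = 6% of high-dose time.
- High end: N = 81 x 0.5 x 0.6 = 24.3, giving 326 person-weeks. 326/(326 + 1000) = 25%.

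This time follows metformin withdrawal in children selected for better control, so its effect on the ratio cannot be signed from the documents.

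**5. What the randomised comparison would offer**

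Children per dose per drug: 81 x q/2, about 20 to 28. At a 20% event rate in both groups, the 95% half-width for the difference is 1.96 x sqrt(2 x 0.2 x 0.8/n): 25 percentage points with n = 20 and 21 with n = 28.

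**The case against.** The strongest reply is that no safety objective asks for low against high dose. The four objectives in Protocol 1.3.3 are framed by drug or by monotherapy, and the dose-against-dose objectives (c, g and k) are efficacy only. Pooling was prespecified, AE rates are not tested (SAP 4.7.1.1), and the dose-at-onset tables are there to account for changes of treatment. This stands: a reader might infer that the plan fails its safety objectives, and it does not. But Protocol 8.4.3.2 does describe those analyses as comparing safety by treatment received, and the tables print one column per dose with no warning.

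A reader might also infer that the main safety results are biased. They are not: the drug-versus-placebo tables use the first randomisation, with versions up to Week 32 and weighted for metformin withdrawal.

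The size of the distortion is assumption-driven. The documents give no AE timing, and a lower base rate softens the ratios. That is why a range is shown.

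Subject listings are sorted by up-titration dose and AE listings show the most recent dose (SAP 4.1.7, 4.7.1.1), so the randomised comparison could be rebuilt by hand. No summary does so.

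The groups are small. That is true, but secondary efficacy comparisons 9 to 11 already rely on the same groups.

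**Conclusion.** The point holds as a gap in the safety presentation. The only planned tables that separate the doses confound dose with time on study, Week 12 response and, later, background metformin. The randomisation that would remove this confounding is used for disposition, demographics and efficacy only.

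If events cluster early, the false high/low ratio is about 0.80-0.85, 0.66-0.74 or 0.48-0.59 for an early rate 1.5, 2 or 3 times the later one. This assumes no true dose effect, 50-70% non-responders, no dropout, no third randomisation, and later first-event rates from 100 down to 10 per 100 patient-years.

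A reader might conclude that the tables will make the high dose look safer. The documents do not support that: early clustering is assumed, and the third randomisation could move the net bias either way. What can be said is that these columns cannot be read as a dose effect.

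**What to change.** - In SAP 8.13 add Safety to the second-randomisation rows, and extend 2.2.3 and Table 24 to match.
- In SAP 4.7 add one descriptive summary per drug on the Up-titration Randomised Subjects Data Set, by dose assigned at Week 14. Cover AEs, SAEs, AEs leading to discontinuation, hypoglycaemia, adjudicated DKA and marked laboratory abnormalities.
- Count onset from the Week 14 dose change, with events on that day going to the new dose as in SAP 4.1.6. Stop at the earliest of the existing Week 32 cut-off, the start of third-randomisation treatment, and the Table 8 post-dose windows.
- Keep the dose-at-onset tables, with a footnote that their dose columns are not randomised groups and differ in time on study.

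The cost is SAP wording and one extra set of tables from data already collected. The summary spans about 18 weeks (Week 14 to Week 32) in about 20-28 children per dose per drug, so intervals will be wide and it can only be descriptive. It describes stepping up against staying on the low dose in Week 12 non-responders, not starting treatment at the high dose.

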The above endpoints will be summarized within each treatment group from the original randomization as follows:

- For subjects initially randomized to the dapagliflozin (or saxagliptin) group, the subjects
 re-randomized to withdraw metformin will be compared to the subjects re-randomized to stay
 on metformin. Separate analyses will be performed for subjects respectively randomized to
 either the dapagliflozin or saxagliptin group.
- For subjects initially randomized to the placebo group, the subjects who were re-randomized
 to switch to dapagliflozin (or saxagliptin) monotherapy will be compared to the subjects who
 were re-randomized to stay on placebo with background metformin. Separate analyses will be
 performed respectively for subjects re-randomized to the dapagliflozin and for those
 re-randomized to the saxagliptin group, using those re-randomized to remain on placebo as
 comparator.

The observed and change from withdrawal baseline in HbA1c and in FPG will be summarized. Percentage of subjects who achieve or maintain an HbA1c level < 7.0% at the end of the withdrawal period will also be summarized.

Time from baseline withdrawal (days) to initiation of glycemic rescue medication or discontinuation of study medication due to lack of efficacy during the randomized withdrawal period will be summarized using Kaplan-Meier estimates.

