4.1.5 Treatment regimens

The following treatment regimens are considered for analysis:

- Low-dose/high-dose: Initial treatment of the low-dose (5 mg of dapagliflozin or 2.5 mg of saxagliptin) followed by up-titrating to the high-dose (10 mg of dapagliflozin or 5 mg of saxagliptin) for those who do not achieve the glycaemic target of HbA1c < 7% at Week 12 (not responding and re-randomised to high-dose) and continuing treatment with the low-dose for those achieving the glycaemic target of HbA1c < 7% at Week 12 (responding and not re-randomised; Groups I & III in [Figure 1](#)).
- Low-dose: Initial treatment of the low-dose (5 mg of dapagliflozin or 2.5 mg of saxagliptin) followed by continuing treatment on the low-dose drug for those who do not achieve the glycaemic target of HbA1c < 7% at Week 12 (not responding and re-randomised to low-dose) and those achieving glycaemic target of HbA1c < 7% at Week 12 (responding and not re-randomised; Groups I & II in [Figure 1](#)).
- Placebo, all subjects randomised to placebo.

Subjects who are receiving background medication with insulin only, or metformin + insulin (and who are therefore not eligible for the third randomisation) will continue with their randomised study medication assigned after the Week 12 assessment in the double-blind LT treatment period. After completion of assessments at Week 26, a subset of eligible subjects who are receiving background medication with metformin only will undergo a third randomisation (randomised withdrawal of background medication) at either Week 32 or Week 40. The following treatment comparisons are considered for this analysis:

- For subjects initially randomised to dapagliflozin (or saxagliptin): Initial treatment of the overall (combined low-dose and high-dose) dapagliflozin (or saxagliptin) with metformin compared to high-dose dapagliflozin (or saxagliptin) without metformin.
- For subjects initially randomised to placebo: Initial treatment of the placebo with metformin compared to high-dose dapagliflozin (or saxagliptin) without metformin.
- For all subjects, regardless of initial randomisation, based on third randomisation (for AE and marked abnormality [MA] laboratory analysis only).

For Week 104 analyses, subjects will be summarised based on both the first and last treatment received and also repeated for the subset of Week 104 completers (subjects who had the Week 104 visit).

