4.6.2.5 Percentage of subjects who initiate glycaemic rescue medication

The number and percentage of subjects who require glycaemic rescue medication during the 52-week treatment period will be provided.

In addition, this analysis will be repeated for the subgroup of subjects on a stable baseline dose of metformin IR or XR (with or without insulin).

4.6.3 Exploratory efficacy analyses for monotherapy assessment during the randomised withdrawal period

These analyses will be conducted during the randomised withdrawal period using the Randomised Withdrawal Subjects Data Set.

The endpoints will be summarised within each treatment group (as defined in Section 2.1) from the original randomisation as follows:

- For subjects initially randomised the dapagliflozin (or saxagliptin) group, the subjects re-randomised to withdraw metformin will be compared to the subjects re-randomised to stay on metformin. Separate analyses will be performed for subjects respectively randomised to either dapagliflozin or saxagliptin group.
- For subjects initially randomised to the placebo group, the subjects who were re-randomised to switch to dapagliflozin (or saxagliptin) monotherapy will be compared to the subjects who were re-randomised to stay on placebo with background metformin. Separate analyses will be performed respectively for subjects re-randomised to

dapagliflozin and for those re-randomised to saxagliptin, using the those re-randomised to placebo as comparator.

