5. INTERIM ANALYSES (NOT APPLICABLE)

6. CHANGES OF ANALYSIS FROM PROTOCOL

Table 12 Changes of analysis from protocol

Section of SAP Affected (If applicable)	Change	Rationale
Section 2.2.7	A PK analysis data set was defined in the SAP, but this isn't mentioned in the study protocol.	It is necessary to have an analysis set defined for the PK data.
Section 4.1.1	The definition of the withdrawal baseline differs between the study protocol and the SAP.	This change was made to align the withdrawal baseline with how we define dose at onset and how to handle scenarios where the randomisation was done on a different date to the main visit.
Section 4.1.10	Fisher's exact test is used instead of logistic regression where there are <5 responders per treatment group.	This analysis was not mentioned in the protocol.
Section 4.1.12	The "wash-out" imputation method is used where there is insufficient data from "retrieved drop-outs".	This analysis was not mentioned in the protocol.

Section of SAP Affected (If applicable)	Change	Rationale
Sections 4.4 and 4.5	The primary efficacy endpoint was updated to use overall treatment and the secondary efficacy endpoints were updated to follow the order/hierarchy of overall, followed by low-dose/high-dose regimen testing, followed by low-dose regimen.	This was due to protocol amendment #6.
Section 4.7.1.1	The protocol states that additional safety analyses will be performed on the Treated Subjects Data Sets on all DKA events but in the SAP, we only present the analysis for adjudicated DKA SAEs.	Additional analyses were only done on confirmed DKAs.
Section 4.10	It was decided that all the TFLs will be produced excluding data collected from Site 4910. In addition, a few analyses will be produced including subjects from Site 4910.	This was due to loss of access to the source data of subjects at Site 4910. This decision was made following investigation by AstraZeneca.
Appendix 8.13	The protocol states that “separate analyses will be performed for subjects respectively randomized to the dapagliflozin or saxagliptin group” while in the SAP, we combine the randomised withdrawal treatment into one analysis table.	Presenting the data this way was more informative.

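### SAP 8.13 pools placebo switchers with drug-arm subjects in its withdrawal-period monotherapy labels, contradicting the within-arm efficacy comparisons in SAP 4.6.3

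*SAP*

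**What the plan says.** SAP 8.13 lists the treatment labels for tables and figures, and SAP 4.1.5 sends the reader there for full detail. The third-randomisation labels are for "Randomised withdrawal subjects analysis set outputs: Disposition, Demographics, Efficacy, Safety". Each drug has one monotherapy label, covering every subject withdrawn from metformin onto that drug. The dapagliflozin definition closes with "or switch from placebo to dapagliflozin 10mg" and the saxagliptin definition with "or switch from placebo to saxagliptin 5mg". The comparator labels are restricted by first randomisation; for dapagliflozin plus metformin the definition is "All 1 st randomisation dapagliflozin subjects randomised at Week 32/40 to remain on background metformin". No label is given for placebo switchers alone.

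The analysis sections say something different:

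- SAP 4.6.3, on withdrawal-period efficacy: "The endpoints will be summarised within each treatment group (as defined in Section 2.1) from the original randomisation as follows". Drug-arm subjects who stop metformin are set against drug-arm subjects who keep it. Placebo subjects who switch are set against those who stay on placebo plus metformin.
- Protocol 8.4.2.3: "The above endpoints will be summarized within each treatment group from the original randomization as follows". It gives each source its own question. The drug arms show what metformin adds in the presence of the drug; the placebo arm compares drug monotherapy with metformin alone.
- SAP 4.1.5 lists the pooled view as a third comparison: "For all subjects, regardless of initial randomisation, based on third randomisation (for AE and marked abnormality [MA] laboratory analysis only".
- SAP 4.7 and 4.7.2.4 extend that third comparison to hypoglycaemia.
- SAP Table 23 splits withdrawal-period efficacy into two columns by first randomisation.

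SAP Table 12 lists 8.13 as a change from the protocol's separate analyses for dapagliflozin and saxagliptin: "in the SAP, we combine the randomised withdrawal treatment into one analysis table".

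**The concern.** A programmer who builds the withdrawal-period efficacy tables from 8.13 gets one monotherapy column per drug, drawn from two different randomisations. That column then stands beside drug plus metformin and placebo plus metformin, and neither is a randomised comparator for all of it.

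The change from withdrawal baseline also differs in meaning between the two sources. Switchers start the study drug and stop metformin together. Drug-arm subjects stop metformin after some 32 to 40 weeks on the drug, and those on the low dose are also moved to the high dose. A pooled mean describes neither change and answers neither of the two questions in Protocol 8.4.2.3.

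**Working it through.** **The plan's own figures.** The documents give no sample size, power or eligibility rate for the withdrawal period, so there is no figure to reproduce for this point. The only power statement (about 80% with 81 per arm, difference 0.75%, SD 1.7%) concerns the primary comparison. It reproduces at 80.2% but plays no part here.

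**Who could be assigned to what (SAP 1.2).**

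| First arm | Third randomisation | Possible groups |
|---|---|---|
| Drug | 1:1 | drug monotherapy; drug + metformin |
| Placebo | 1:1:1 | dapagliflozin monotherapy; saxagliptin monotherapy; placebo + metformin |

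A placebo subject cannot be assigned to drug + metformin, and a drug-arm subject cannot be assigned to placebo + metformin. Each pooled contrast therefore includes subjects who had no chance of being in its comparator.

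**Share of switchers in the pooled label.** Let k be eligible placebo subjects per eligible subject on the given drug. Per eligible drug-arm subject, 1/2 enters the label from the drug arm and k/3 from placebo, so

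s = (k/3) / (1/2 + k/3).

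The documents do not give k. Over an assumed range:

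- k = 0.25: 0.0833/0.5833 = 14%
- k = 0.5: 0.1667/0.6667 = 25%
- k = 1: 0.3333/0.8333 = 40%
- k = 1.25: 0.4167/0.9167 = 45%

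**What pooling does to a mean.** Let D be the mean change in switchers minus the mean change in drug-arm withdrawers. The pooled mean is the drug-arm mean plus s × D. Relative to the within-arm contrasts, the contrast with drug + metformin moves by s × D, and the contrast with placebo + metformin moves by (1 − s) × D in the opposite direction. At k = 1 these are 0.40 × D and 0.60 × D. D is not in the documents. For assumed values of 0.25, 0.5 and 1.0 percentage points of HbA1c, the shifts are 0.10 and 0.15, 0.20 and 0.30, and 0.40 and 0.60 points. These show scale only; they are not estimates.

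**After the label is split.** The share of switchers in the contrast with drug + metformin is 0%, and so is the share of drug-arm subjects in the contrast with placebo + metformin. Both are then randomised comparisons.

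**The case against.** The strongest reply is that 8.13 is a list of labels, not an instruction to run contrasts. The contrasts are set in SAP 4.6.3, 4.1.5 and Table 23, all by first arm. Other sections use the third-randomisation groups in split form: disposition is shown by first and third randomisation (SAP 4.2.1), and laboratory values over time, vital signs and body measurements use only the first two comparisons (SAP 4.7.3, 4.7.4, 4.7.6). The table specifications are separate documents (SAP 4.1) and may already split the columns. This stands in part: pooling is what 8.13 states, not a certain outcome. But 8.13 names efficacy, offers no label for switchers and is cited as the full detail on labels, so the contradiction remains.

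A second reply is that Table 12 declares the change. It declares a single table in place of separate analyses by drug. One table can hold separate columns, and the entry does not say that switchers are merged with drug-arm subjects or that the 4.6.3 contrasts are dropped.

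A third is that split columns will be small. If 10% to 40% of 81 subjects per arm were eligible (an assumption), about 3 to 11 would switch to each drug (81 × 0.10/3 = 2.7; 81 × 0.40/3 = 10.8). That is true, but a larger column with no randomised comparator does not repair it.

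A reader might also infer that pooling flatters monotherapy, because switchers gain a drug while drug-arm subjects merely lose metformin. The documents do not support this. Switchers lose metformin too, low-dose drug-arm subjects are up-titrated, and no withdrawal-period effect is given from which to sign D.

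**Conclusion.** The contradiction is real. SAP 8.13 pools placebo switchers with drug-arm subjects for outputs that include efficacy, while SAP 4.6.3, SAP 4.1.5, SAP Table 23 and Protocol 8.4.2.3 keep efficacy within the first arm. As written, the tables depend on which section the programmer follows, and under 8.13 neither contrast is randomised.

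Switchers would be 40% of the pooled group at k = 1 and 25% at k = 0.5. The formula follows from the stated ratios; k is assumed. The direction and size of any bias cannot be known from the documents.

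A reader might go on to doubt the trial's main results. That does not follow. The withdrawal-period endpoints are exploratory and not statistically tested (SAP 4.6); they are summarised descriptively without imputation, with Kaplan-Meier estimates for time to rescue or discontinuation (SAP 4.6.3.1 to 4.6.3.4). The primary and secondary analyses at Week 26 precede the third randomisation and are untouched.

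**What to change.** In SAP 8.13, split each monotherapy label by first randomisation: drug to monotherapy, and placebo to monotherapy. Use the split labels for efficacy and for the safety outputs restricted to the first two comparisons of SAP 4.1.5. Place each beside its own randomised comparator, in one table if that is preferred.

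Keep the pooled label only for the third comparison, in adverse events, hypoglycaemia and marked laboratory abnormalities. Hypoglycaemia belongs on that list because SAP 4.7 and 4.7.2.4 plan it; add it to the restriction in SAP 4.1.5, which omits it.

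Reword the Table 12 entry to say that both drugs and both source arms appear in one table in separate columns, and check the table specifications against it. The cost is labels, column layout and a few lines of SAP text. No new data or analysis method is needed.
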